**Table 7 Censoring Rules for Subjects Unblinded Prior to Protocol Version 3.0**

Analysis	Treatment Received in CV-NCOV-002	Alternate Licensed/Authorized Vaccine Received?	Censoring Rule
Safety	CVnCoV	No Yes	Censored at the first day after unblinding
	Active Control	No Yes	
Immunogenicity	CVnCoV	No	Analyzed as planned
		Yes	Censored at the first day after receiving the alternate licensed/authorized vaccine.
	Active Control	No	Analyzed as planned
		Yes	Censored at the first day after receiving the alternate licensed/authorized vaccine

The following details are to be followed regarding censoring the day after unblinding:

- Unblinding day ( = Pacific Time Zone) must be adjusted to the subject's time zone.
- Unblinding time does not matter for anything apart from the above time zone normalization. (As case start time is not collected.)
- If the case start day and the unblinding day occur on the same day the case will count for the analysis. (Censoring starts at the day after the unblinding.)

The following details are to be followed regarding censoring the day after receiving the alternate licensed/authorized vaccine:

- Times are not relevant as neither alternate licensed/authorized vaccine time nor case start time are collected.
- If alternate licensed/authorized vaccine date is complete then censoring starts at first day after the alternate licensed/authorized vaccine day.
- If alternate licensed/authorized vaccine date is incomplete (only day missing) then censoring starts after this month.
- If alternate licensed/authorized vaccine date is incomplete (month missing, year available) then censoring starts after this year.
- If alternate licensed/authorized vaccine date is completely missing then no censoring can be made.

As these imputations of incomplete licensed vaccine dates are not an ideal solution this is only to be considered as a fallback solution in case complete licensed vaccine dates cannot be retrieved and an interim workaround for unclean data during study conduct.

All incomplete or missing licensed vaccine dates need to be queried.

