### 9.4 Estimands

ENDPOINTS (subject level)	ESTIMANDS (population level)
Primary Safety	

The frequencies, intensities, and duration of solicited local AEs on Day 1 and Day 29 and the following 7 days by dose and group.
 
The frequencies, intensities, duration, and relationship to trial vaccination of solicited systemic AEs on Day 1 and Day 29 and the following 7 days by dose and group.
 
The occurrence, intensity and relationship to trial vaccination of unsolicited AEs on each vaccination day and the following 28 days by dose and group.
 
The occurrence and relationship to trial vaccination of SAEs and AESIs throughout the trial.
	
Safety set. Subjects who were unblinded and/or received an authorized/licensed COVID-19 vaccine will be censored at the day after unblinding and/or vaccination receipt.
 
The number and percentage of subjects overall and by dose level:
 
Each solicited local AE within 7 days after each trial vaccination by intensity and overall.
 
Each solicited systemic AE within 7 days after each trial vaccination by intensity, by relationship to trial vaccine and overall.
 
The mean duration in days by group with standard deviation of solicited AEs (within the solicited period, total duration).
 
At least 1 unsolicited AEs, at least 1 grade unsolicited AEs and each unsolicited AEs by SOC/PT occurring within 28 days after each trial vaccination and overall by causal relationship to trial vaccine and overall.
 
At least 1 SAE, or at least 1 AESI to vaccine overall by causal relationship to trial vaccine and overall.

ENDPOINTS (subject level)	ESTIMANDS (population level)
Primary Immunogenicity	

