	Safety set. Applicable for subjects who received a booster dose at day 57 or day 180. Subjects unblinded and/or received an authorized/ licensed vaccine during the course of the trial will be censored at the day after unblinding or receipt of authorized/ licensed vaccine (whichever is earlier).

ENDPOINTS (subject level)	ESTIMANDS (population level)

 
The frequencies, intensities, and duration of solicited local AEs on the day of the booster administration and the following 7 days by group.
 
The frequencies, intensities, duration, and relationship to trial vaccination of solicited systemic AEs on the day of the booster administration and the following 7 days by group.
 
The occurrence, intensities and relationship to trial vaccination of unsolicited AEs on the day of the booster administration and the following 28 days by group.
 
	
The number and percentage of subjects by group reporting:
 
 
Each solicited local AE within 7 days after each trial booster vaccination by intensity and overall
 
Each solicited systemic AE within 7 days after each trial booster vaccination by intensity, by relationship to trial vaccine and overall.
 
At least 1 unsolicited AEs, at least 1 grade 3 unsolicited AEs and each unsolicited AEs by SOC/PT occurring within 28 days after each trial booster vaccination and overall by causal relationship to trial vaccine and overall
 
The mean duration in days by group with standard deviation of solicited AEs (within the solicited period, total duration).
 

Secondary Immunogenicity	

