## 10.8 Censoring Rules for Subjects Unblinded and/or Treated with Alternate Licensed/Authorized Vaccine

Since the efficacy results from Trial CV-NCOV-004 are available and all subjects in this trial are currently eligible to receive a licensed/authorized vaccine, all subjects in this trial will be unblinded following protocol version 3.0. Hence, all subjects will be unblinded prior end of the trial, and their data will be censored in all analyses. The below rules are still applicable as subjects could request unblinding or became eligible to receive a licensed/authorized vaccine prior to the protocol V3.0.

The following censoring rules will be applied to these subjects to avoid any study bias.

- Subjects who are unblinded will be censored for the safety endpoints at the first day after unblinding. Any related follow-up data that is collected from censoring time point forward will be included in the listings output.
- Subjects who are unblinded but decide not to receive the alternate licensed/authorized vaccine and to stay in the study will be analyzed for immunogenicity as planned.
- Subjects who are unblinded, but decide to receive the alternate licensed/authorized vaccine, will have their immunogenicity data censored at the first day after receiving the alternate licensed/authorized vaccine. However, any related follow-up data that is collected from this time point forward will be included in the listings output.
- Subjects who received an alternate licensed/authorized vaccine without or before being unblinded will be censored for safety and immunogenicity at the first day after receiving the alternate licensed/authorized vaccine. As described above, data collected from the censoring timepoint forward will be included in the listings output.

This is summarized in Table 7.

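### SAP Table 7 and section 10.8 give two different safety censoring dates for a subject who took a licensed COVID-19 vaccine and was later unblinded before protocol version 3.0

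*SAP*

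**What the plan says.** SAP section 10.8 sets the censoring rules in four bullets. The first is general: "Subjects who are unblinded will be censored for the safety endpoints at the first day after unblinding". The second and third deal with immunogenicity after unblinding. The fourth covers the reverse order of events, a licensed vaccine taken "without or before being unblinded will be censored for safety and immunogenicity at the first day after receiving the alternate licensed/authorized vaccine". The section then states: "This is summarized in Table 7".

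Table 7 is titled "Censoring Rules for Subjects Unblinded Prior to Protocol Version 3.0". Its only safety rule is "Censored at the first day after unblinding". I read the safety block as one merged cell covering both arms and both answers to whether a licensed vaccine was received. On any reading of the layout, no safety entry refers to the vaccine date. The immunogenicity rows do separate yes from no, and they use the vaccine date for yes.

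In SAP section 9.4, the secondary safety estimand has subjects "censored at the day after unblinding or receipt of authorized/ licensed vaccine (whichever is earlier". The primary safety and infection estimands say that subjects "will be censored at the day after unblinding and/or vaccination receipt". Vaccination is therefore a censoring event there too, but the order is not spelled out.

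**The concern.** A subject who took a licensed vaccine and was unblinded later, before version 3.0, meets two rules. The first bullet and Table 7 censor at unblinding. The fourth bullet and the secondary safety estimand censor at the vaccine. The first bullet makes no exception for the fourth, and the table offered as the summary drops the fourth bullet on the safety side.

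A summary table is a natural source for programming. If it is followed, events after another COVID-19 vaccine are attributed to a trial arm, although section 10.8 gives avoidance of bias as the reason for censoring. The exposed outputs have no short window: SAEs and AESIs (primary endpoints for the whole trial), and the medically attended and all-reported AE summaries in SAP section 12.8.1. COVID-19 disease is itself an AESI. The 7-day solicited and 28-day unsolicited summaries are touched only if the licensed vaccine falls inside the window.

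**Working it through.** There is no figure in the plan to reproduce. The check is to apply each rule to each ordering of two dates.

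Let U be the day of unblinding and V the day of the licensed vaccine. The first censored safety day is:

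- Section 10.8, with the fourth bullet taking precedence over the first: V + 1 if V is before U or there is no U; otherwise U + 1.
- Table 7: U + 1 in every case.
- Secondary safety estimand: min(U, V) + 1.

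| U | V | Section 10.8 | Table 7 | Earlier of the two |
|---|---|---|---|---|
| 200 | none | 201 | 201 | 201 |
| 200 | 230 | 201 | 201 | 201 |
| 200 | 200 | 201 | 201 | 201 |
| 200 | 170 | 171 | 201 | 171 |
| 200 | 110 | 111 | 201 | 111 |
| none | 170 | 171 | no rule | 171 |

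The days are illustrative. The rules part only when the vaccine precedes unblinding, or when there is no unblinding. In the first case Table 7 keeps U − V extra days in the summaries: 200 − 170 = 30 and 200 − 110 = 90. In the second case it has no entry.

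Scale, on assumed inputs:

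- Planned subjects, from SAP Table 2: 603 + 10 + 10 + 40 = 663.
- f: the share of the 663 who were vaccinated first and then unblinded before version 3.0. The documents do not give it; I assume 5% to 20%.
- g: the gap U − V. This is not given either; I assume 30 to 90 days.

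Extra person-years = 663 × f × g / 365.25.

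- Low: 663 × 0.05 × 30 / 365.25 = 2.7.
- High: 663 × 0.20 × 90 / 365.25 = 32.7.

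Against planned follow-up of 663 × 393 = 260,559 person-days, these are 994.5 / 260,559 = 0.4% and 11,934 / 260,559 = 4.6%. The result is proportional to f, so at f = 1% the lower figure falls to 2.7 / 5 = 0.5 person-years.

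Check of the remedy: with min(U, V) + 1 in the table, the case U = 200, V = 170 moves from day 201 to day 171. Table, text and secondary estimand then agree in every row where both dates exist. An added row covers the last case.

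**The case against.** The strongest reply is that the plan already handles this ordering. The fourth bullet addresses it by name, includes safety, and is more specific than the first. The secondary safety estimand agrees, and the other two estimands name vaccination as a censoring event. The operating notes under Table 7 discuss vaccine-date censoring in terms of case start times, which is not the language of immunogenicity samples. On this view the table is merely an incomplete summary of a clear rule, in a trial with descriptive analyses only.

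Much of that stands. The intended rule is hardly in doubt, and harm arises only if a programmer follows the table or the first bullet. The text still contains a rule that gives the wrong date for this subject, and nothing says which source prevails.

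Three stronger readings are tempting, and the documents do not support them.

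- A reader might infer that everyone vaccinated elsewhere before being unblinded is affected, since version 3.0 unblinds all subjects. The title of Table 7 limits it to earlier unblindings. For the others, and for subjects never unblinded, the table is silent and the fourth bullet governs.
- A reader might infer that follow-up stops. It does not: later data stay in the listings, and subjects are asked to remain for safety follow-up.
- A reader might infer that all the estimands state the earlier date. Only the secondary safety estimand does so explicitly.

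**Conclusion.** The inconsistency is real and narrow. It concerns safety summaries for subjects who received a licensed vaccine first and were unblinded afterwards but before protocol version 3.0. For each such subject, Table 7 keeps U − V days that the fourth bullet and the secondary estimand remove. The documents do not give the number of such subjects or the length of the gap. The 2.7 to 32.7 person-years above rest wholly on assumed values, and the restriction to early unblindings suggests a small number.

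The scale figures should not be turned into a claim about vaccine-related SAEs. At an assumed 3 SAEs per 100 person-years they would give 2.7 × 0.03 = 0.08 to 32.7 × 0.03 = 0.98 SAEs of any cause. Relatedness is a separate investigator judgement, and Appendix 10 of the protocol lists concomitant vaccination among the alternative causes to be weighed. This is a small correction worth making because it is cheap, not a threat to the trial's conclusions.

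**What to change.** 1. In the Table 7 safety entries for subjects who received a licensed vaccine, in both arms, start censoring on the day after unblinding or after licensed-vaccine receipt, taking the earlier date.
2. Add a Table 7 row for a licensed vaccine received without unblinding, with censoring from the day after the vaccine. Adjust the title so that the row falls within its scope.
3. Make the first bullet of section 10.8 expressly subject to the fourth.
4. In section 9.4, state the earlier-date rule in the primary safety and infection estimands, as the secondary safety estimand already does.

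Incomplete licensed-vaccine dates stay under the existing query and fallback rules below Table 7, including the provision that a wholly missing date cannot be used for censoring.

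The cost is SAP wording and a check that the derivation of the safety censoring date matches it. No new data are needed, because the SAP already relies on both dates. SAP section 6.0 provides for an amended version to be approved before final database lock.

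### Unresolved licensed-vaccine dates are taken as late as possible, or not censored at all, so any error keeps data after another COVID-19 vaccine in the analysis

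*SAP*

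**What the plan says.** SAP 10.8 gives the reason for censoring: "The following censoring rules will be applied to these subjects to avoid any study bias". With a complete date, "then censoring starts at first day after the alternate licensed/authorized vaccine day". The estimands in SAP 9.4 likewise censor on the day after receipt.

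The details under Table 7 then cover poor dates:

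- Day missing: "If alternate licensed/authorized vaccine date is incomplete (only day missing) then censoring starts after this month".
- Month missing: "If alternate licensed/authorized vaccine date is incomplete (month missing, year available) then censoring starts after this year".
- No date: "If alternate licensed/authorized vaccine date is completely missing then no censoring can be made".

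The SAP concedes that this is not ideal. It describes the rules as "only to be considered as a fallback solution in case complete licensed vaccine dates cannot be retrieved" and as a stopgap while data are still unclean, and adds: "All incomplete or missing licensed vaccine dates need to be queried". It plans no sensitivity analysis for them.

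Two other provisions limit the effect. On safety: "Subjects who are unblinded will be censored for the safety endpoints at the first day after unblinding", whether or not another vaccine was taken. On immunogenicity, protocol 9.2 and SAP 10.6 stop sampling and analysis once a licensed vaccine has been received.

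**The concern.** The censoring is there to keep another vaccine's effects out of the results. All three fallback rules can be wrong in one direction only: they count post-vaccine time as trial-vaccine or control time. Reactions to the other vaccine could be reported under CVnCoV or control, follow-up protected by the other vaccine could enter the infection counts, and antibody raised by it could enter late serology.

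The SAP also dates the same injection in two ways. Licensed vaccines are concomitant vaccinations (ATC J07, SAP 12.6). For a concomitant medication with a missing day, in a month after the trial-vaccination month, SAP 10.3 imputes the first of the month. SAP 10.8 uses the end of that month for censoring.

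**Working it through.** The plan states no figure on this point, so there is none to reproduce. The check is date arithmetic plus a reading of which data the rules reach.

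**1. Days retained in error.** Let V be the true vaccine date. Correct censoring starts at V + 1. Excess days = fallback start − (V + 1).

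- Day missing, V on day k of a month of L days: excess = (L + 1) − (k + 1) = L − k. The range is 0 to 30. The mean over all dates in 2021 is (7 × 465 + 4 × 435 + 378) / 365 = 5,373 / 365 = 14.7 days.
- Month missing, V on day k of a 365-day year: excess = 365 − k. The range is 0 to 364 and the mean 182 days, before any limit from follow-up or unblinding.
- No date: nothing is censored on account of the vaccine.

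**2. Is 364 days attainable?** It needs V = 1 January and follow-up through 31 December. Nominal Day 393 is Day 1 + 392 days. For Day 393 to fall on or after 31 December 2021, Day 1 must be 4 December 2020 or later, which makes 1 January 2021 Day 29 or earlier. The +30-day window for the last contact moves this only to about Day 59. A licensed vaccine that early would fall around the primary doses, and exclusion criterion 2 bars planned vaccines within 28 days of trial vaccination. So 364 days is an arithmetic limit, not a realistic size.

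**3. A more realistic illustration.** The documents give no enrollment dates. Assume Day 1 between 1 October 2020 and 1 February 2021, so that Day 393 falls between 28 October 2021 and 28 February 2022.

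- A year-only date of 2021 produces no censoring up to Day 393 for anyone with Day 1 on or before 4 December 2020.
- With a true vaccine date of 1 June 2021, 149 days (to 28 October) to 213 days (to 31 December) are retained, unless earlier unblinding ends the safety data.

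**4. Which data are reached.**

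- *Safety.* A subject unblinded first is censored by the unblinding date. The fallback matters only for those vaccinated while still blinded, and only until unblinding (or the last contact, if sooner). Solicited (7-day) and unsolicited (28-day) windows are short. Trial-long SAEs and AESIs, which include COVID-19 disease, and RT-PCR infection counts are the exposed endpoints.
- *Immunogenicity.* Unblinding does not censor here, so the vaccine date decides. Primary endpoints end at Day 43. Later humoral endpoints are for booster recipients, planned as 30 + 30 + 30 = 90 subjects. The instruction to stop sampling came with protocol version 3.0 (3 December 2021), so earlier post-vaccine samples may exist. SAP 12.9.1 analyses all available time points.

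**5. Can a missing date be bounded?** Yes. Protocol Table 1 records concomitant vaccination at nearly every contact, including Days 120, 180, 270 and 393. The last contact with no licensed vaccine recorded gives a lower bound. The nominal gaps are 120 − 57 = 63, 180 − 120 = 60, 270 − 180 = 90 and 393 − 270 = 123 days.

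**The case against.** The strongest reply is that this is an acknowledged last resort. All such dates are queried, the analysis is descriptive, concomitant vaccinations and data after the censoring point are listed, and nobody may be affected. This stands as a limit on size. It does not justify the direction: the rule governs what queries cannot resolve and any interim snapshot taken before they are answered.

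A second reply is that retaining events is the cautious choice for safety, and that the earliest date makes the opposite one-sided error. It is true that earliest-date censoring can remove genuine pre-vaccine events, and without a floor it could cost up to 30 or 364 valid days. That is the reason for a last-contact floor and for reporting both versions.

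A reader might infer more than the documents support:

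- *That all later safety data are contaminated when the date is missing.* Unblinding ends the safety data whatever the vaccine date.
- *That control-arm immunogenicity is materially affected.* Controls have no planned humoral endpoint after Day 43.
- *That the stop-sampling instruction fails without an exact date.* It turns on whether a licensed vaccine has been received, which a site can know without the date. The date is needed only to classify samples already taken.

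**Conclusion.** The concern holds in limited form. The three rules err only towards keeping post-vaccine data, contrary to the purpose stated in SAP 10.8 and to the estimands. It is also not correct that nothing can be done when the date is missing, because the contact schedule bounds it.

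Per affected subject, the retained time is 0 to 30 days with the day missing and up to several months with the month missing. With no date, it is all remaining follow-up for immunogenicity, or the time to unblinding for safety. The several-month figure rests on the assumed enrollment dates and the illustrative June vaccination. How many subjects are affected is not stated, so the effect on any table cannot be sized and may be modest. The documents do not support reading this as nearly a year of contaminated data, or as undermining the trial's main reactogenicity or Day 43 results.

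**What to change.** For dates that queries cannot resolve, replace the three bullets in SAP 10.8:

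- **Partial date:** censor from the earliest date compatible with it (first of the month, or 1 January), but not before the day after the last contact at which no licensed vaccine was recorded.
- **Fully missing date:** censor from the day after that contact.

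Keep the later data in the listings. Report the present latest-date and no-censoring rule as a sensitivity analysis, so that the two versions bound the effect and no safety event is hidden. State how many subjects fall under each rule.

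The cost is three SAP bullets and one extra run, with no new data. In affected subjects, valid pre-vaccine data of up to one gap between contacts, about 60 to 123 days after Day 57, leave the main analysis.

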## 10.9 Adjudication of COVID-19 Cases

An independent committee of clinicians will be formed to adjudicate COVID-19 cases. The committee will be blinded to the treatment assignment of the subject. The cases will be adjudicated by the members with respect to the following questions consistent with the endpoints of the trial.

- Is the case a virologically-confirmed case of COVID-19 defined as a positive SARS-CoV-2 specific RT-PCR test in a person with clinically symptomatic COVID-19?
- Was the symptom onset of the case  $\geq 15$  days following the second vaccination? Or did it occur before 15 days following the second trial vaccination?
- Was the subject naïve or non-naïve to SARS-CoV-2 at baseline and Day 43? (defined as being seronegative or seropositive to the SARS-CoV-2 N protein).
- Was the subject 18 to 60 years of age or  $\geq 61$  years of age?
- Was it a mild, moderate, or severe case of COVID-19 based on the information available on the AESI form (investigator judgement)?
- Was the subject hospitalized? Was the subject admitted to the intensive care unit?
- Did the subject die? Due to COVID-19 or other cause?

These data will be listed only.

